During the past 20 years or so, there have been anecdotal reports of PCT resolving with successful anti-viral therapy of CHC, although there also have been reports of such therapy precipitating or worsening PCT ([name] et al, 2013). Because active cutaneous lesions of PCT are generally more symptomatic than CHC, which usually occurs with few, if any, symptoms until late in the course of advanced liver disease, and because typically PCT is successfully treated within about 6 to 7 months, either with iron reduction or one of the 4-aminoquinolones (Singal et al, 2012), the usual recommendation has been first to treat active PCT and thereafter to treat CHC. Until

recently, therapy of CHC has been longer (usually at least 48 weeks), less often successful and fraught with adverse effects, especially related to the use of interferon alpha, which has been the cornerstone of treatment. However, during the past few years, newer and more effective oral therapies for CHC, with far fewer and less severe side-effects have been approved by the US FDA, the EMA, and other regulatory agencies. In particular, sofosbuvir (Sovaldi) with interferon and ribavirin or with simeprevir (Olysio), and more recently, the combination of ledipasvir + sofosbuvir (Harvoni) (Gilead Sciences) have proven highly effective and to produce far fewer severe adverse effects than the earlier therapeutic regimens based upon interferon (usually in combination with ribavirin) (Syllabus of Post-Graduate Course and presentations at annual meeting of AASLD, Nov 7-11, 2014, Boston, MA). Other combinations of all oral, direct-acting antivirals have recently been approved (e.g., Viekira Pak, Abbvie; Mavyret, Abbvie; Zepatier, Merck) and/or are in late-stage clinical trials.

Because treatment for CHC is now highly successful within as short a time as 8-12 weeks and with few adverse effects, it is reasonable to consider this treatment first in patients with both CHC and PCT. However, experience is needed with a reasonable number of patients in order to validate this approach, and in particular to demonstrate that time to remission is as rapid and that remission of PCT is as durable following therapy with Harvoni as with phlebotomy or (hydroxy) chloroquine. Also, PCT is a heterogeneous, multifactorial disease, and it is important to ascertain whether other co-existing susceptibility factors influence response to a new treatment approach and durability of remission.

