The Office of Rare Diseases (ORD) of the National Institutes of Health (NIH) established a Rare Diseases Clinical Research Network (RDCRN) in collaboration with other NIH Institutes and has funded several rare diseases clinical research consortia and one Data Management and Coordinating Center (DMCC). The Porphyrias Consortium was created as part of the RDCRN, to study the human porphyrias.

4. Study Design and Methods

This will be a one arm, open-label non-inferiority study of Harvoni for treatment of PCT complicating chronic hepatitis C infection caused by HCV genotypes for which Harvoni is approved as therapy, compared to a performance goal of a 50% remission rate at 7 months. This performance goal is based on recently published results from our Consortium (Singal et al, 2012), in which the median time to remission for subjects treated either with phlebotomy or hydroxychloroquine was 7 months, and on expert consensus that if Harvoni demonstrates a median time to remission of 7 months, porphyrias experts would consider using Harvoni over phlebotomy or hydroxychloroquine as a first line of treatment for PCT patients with Hepatitis C. Our aim is to be as inclusive as possible, so that the results will be as generalizable as possible to regular clinical practice. Comparison of response rates, both for amelioration of PCT (the primary endpoint) and for cure of HCV infection (a secondary

endpoint) will be by comparison to recently published results from our Consortium (Singal et al, 2012) and elsewhere (results of recent trials of Harvoni for treatment of chronic hepatitis C).

Adult subjects, of either gender with well-established PCT, who also have CHC due to an HCV genotype 1, 4, 5, or 6, for which Harvoni is approved as therapy, will be invited to take part. PCT patients with CHC typically have additional susceptibility factors, such as alcohol use, estrogen exposure, smoking, *HFE* mutations, *UROD* mutations or HIV infection ([name] et al, 1998, 2013; Egger et al, 2002), and none of these will be reasons for exclusion. Subjects previously treated for PCT and/or HCV infection will be eligible, provided they meet the current criteria for inclusion and exclusion.

Assessment of Stage of Liver Disease:

Cirrhosis will be considered to be present according to the following two-tiered approach:

Stage 1—based upon historical data:

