5.9 Quality Control: Study Related Procedures

The standard laboratory measures will be performed at each Covance Central Laboratory. Porphyrin measurements will be performed in the CLIA certified laboratory of [name], University of Texas Medical Branch, Galveston, TX (see Appendix I for processing instructions).

The investigational pharmacy at each site will be responsible for drug accountability while the investigators/coordinators will be responsible for compliance of the subjects. The Investigational Drug Service at Wake Forest University will serve as the coordinating pharmacy for this study.

6. Statistical Considerations

Primary endpoint: The primary endpoint is resolution of active PCT, defined as normalization of plasma porphyrins (less than 0.9 mcg/dL) by 7 months after the start of therapy. The primary hypothesis will be assessed by computing the exact (i.e., based on the binomial distribution) lower one-sided 95% confidence bound for the proportion of patients whose PCT resolves by 7 months. If this lower confidence bound exceeds 0.40 (the performance goal of 0.50 minus the non-inferiority margin of 0.10) then Harvoni will be declared non-inferior to the performance goal. Seven months has been chosen based upon recent results comparing iron reduction and hydroxychloroquine as therapy for PCT (Singal et al, 2012) and on the consensus of the investigators of the Porphyrias Consortium that a median time to resolution of 7 months would cause them to consider using Harvoni over phlebotomy or hydroxychloroquine as a first line of treatment for PCT patients with Hepatitis C.

Patients missing primary endpoint data are a potential problem in all clinical trials, with the potential for biased inference increasing with the amount of missing outcome data. We will report reasons for missing data, and examine the effect that any missing data might have on results via sensitivity analysis of augmented data sets (for example, best-case or worst-case scenarios). Patients missing the trial's primary endpoint will be included in the analysis by modern imputation methods for missing data.

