If data are missing due to severity of illness, the patient will be counted as a treatment failure (i.e. resolution not achieved). Patients with missing primary outcome data not due to severity of illness will have their 7 month resolution status imputed via multiple imputation assuming that the data are missing at random (i.e. the missing nature of the variable is independent of the value of the variable given the observed data). The specific imputation model to be used will be determined prior to examination of any outcome data, but will include any measured plasma porphyrins from baseline to 6 months. Imputed data will be rounded to 0 (failure/resolution not achieved) or 1 (success/resolution achieved).

After the imputations are completed, all of the data (complete and imputed) will be combined and the analysis performed for each imputed-and-completed dataset. Rubin's method of multiple (i.e., repeated) imputation will be used to estimate treatment

effect. We propose to use 15 datasets (an odd number to allow use of one of the datasets to represent the median analytic result).

Secondary Endpoints:

Time to resolution of active PCT, defined as normalization of plasma porphyrins (less than 0.9 mcg/dL): The median time to resolution by this definition will be computed using Kaplan-Meier estimation and compared descriptively to the median time to resolution reported by standard therapies.

Time to resolution of active PCT, defined as cessation of any new blisters or bullae: Complete resolution of skin manifestations is expected to occur later than normalization of plasma porphyrins, because it takes time for healing of the skin fragility that predisposes of blister formation to occur. The median time to resolution by this definition will be computed using Kaplan-Meier estimation and compared descriptively to the median time to resolution reported by standard therapies.

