Complete Biochemical remission of PCT: Complete biochemical remission of PCT will be measured as a decrease of the sum of urinary uro- and hepta-carboxyl porphyrins to less than 100 mcg/g creatinine, and a normal urine porphyrin HPLC pattern, defined as the total of highly carboxylated porphyrins (uro- and heptacarboxyl-porphyrins) being less than that of coproporphyrins, and absence of a fluorescence peak by fluorescence scanning. The proportion of patients who achieve complete biochemical remission by the end of study period will be computed and the median time to resolution by this definition will be computed using Kaplan-Meier estimation. Because of underlying liver disease and/or possible continuing alcohol use, total urinary porphyrins may remain elevated, due to increased coproporphyrins. We will explore whether and to what extent total urinary porphyrins may remain elevated, due to increased coproporphyrins descriptively in these subjects.

Cure of CHC: Cure of CHC will be defined as no detectable HCV RNA at end of treatment (EOT) and persisting for at least 12 weeks after EOT, now taken as usual definition of sustained virological response (SVR). The proportion of patients who achieve CHC cure will be reported.

Sample Size: The primary study hypothesis is that the proportion of patients whose PCT resolves by 7 months will be non-inferior to the performance goal of 50%. This performance goal is based on previously published data that reported a median time to resolution between 6-7 months for PCT patients undergoing treatment with iron reduction by therapeutic phlebotomies or hydroxychloroquine (Singal et al, 2012). The non-inferiority margin will be set to 10%; a difference from the performance goal judged to be both clinically acceptable and well within the margin needed to assure that the performance of Harvoni is at established levels of benefit from conventional therapies. Thus, the null hypothesis tested by this study is $H_0: \pi \leq 0.40$, against the alternative hypothesis $H_1: \pi > 0.40$.

Sample size requirements are based on an exact test of a binomial proportion. Assuming that the study drug has a true success probability of 58%, 49 subjects yield 80% power to reject the null hypothesis at a one-sided significance level of 0.05.

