The null hypothesis would be rejected at the final analysis if 26 or more successes out of 49 subjects were observed (an observed success rate of 53.1%). The power of the test assuming a true success rate of 58% for Harvoni is 80.2%. Operating characteristics for the decision rule corresponding to the final analysis are given below (Table 3).

Table 3: Operating characteristics for the decision rule (Final analysis)

True Harvoni success rate (π)	Prob (26 or more successes π , N=49)
0.40	0.0434
0.45	0.1609
0.50	0.3877
0.55	0.6627
0.60	0.8718
0.65	0.9695

7. Data Management

As much as possible, data quality is assessed at the data entry point using intelligent on-line forms via the DMCC. Data element constraints; whether independent range and/or format limitations or 'relative' referential integrity limitations can be enforced by all methods employed for data input. QA reports assess data quality post-data entry. As we note, data quality begins with the design of the data collection forms and procedures and incorporates reasonable checks to minimize transcription and omission errors. Of the more important quality assurance measures are the internal validity checks for reasonableness and consistency. In addition to those described above, we propose to build these checks into the initial tables and cross tabulations that should reveal any remaining data quality issues. The NIH Program Staff, the DMCC, and Porphyrias Consortium staff are responsible for assuring and monitoring data quality.

All study data will be collected via systems created in collaboration with the RDCRN Data Management and Coordinating Center and will comply with all applicable guidelines regarding patient confidentiality and data integrity.

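### Do the Table 3 entry at a true rate of 0.40 and the two wordings of the published median put the primary test in doubt?

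*Combined protocol and SAP*

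**What the plan says.** The primary analysis in Section 6 computes the exact one-sided 95% lower confidence bound for the proportion resolved by 7 months. If the bound exceeds 0.40 (the goal of 0.50 less the margin of 0.10), "then Harvoni will be declared non-inferior to the performance goal". The equivalent count rule under Sample Size is rejection if "26 or more successes out of 49 subjects were observed", with stated power of 80.2% at a true rate of 58%. The plan then says: "Operating characteristics for the decision rule corresponding to the final analysis are given below (Table 3"). Table 3 gives the probability of meeting that rule at six true rates. Its first row, at 0.40, reads 0.0434.

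The basis of the 50% goal appears in several places, all citing the same Consortium study:

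- Section 4 (Study Design and Methods): "the median time to remission for subjects treated either with phlebotomy or hydroxychloroquine was 7 months".
- Section 6, Sample Size: "previously published data that reported a median time to resolution between 6-7 months".
- Section 3 (Background), which does not call the figure a median: "typically PCT is successfully treated within about 6 to 7 months, either with iron reduction or one of the 4-aminoquinolones".
- Section 6, Primary endpoint, adds a consensus of the Consortium's investigators that "a median time to resolution of 7 months would cause them to consider using Harvoni over phlebotomy or hydroxychloroquine" as first-line treatment.

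Section 2 (Specific Aims) describes the aim as testing non-inferiority to published remission times of the standard treatments. Under Secondary Endpoints, the Kaplan-Meier median is only "compared descriptively to the median time to resolution reported by standard therapies".

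**The concern.** There are three reasons to stop here.

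1. The 0.40 row of Table 3 is the actual Type I error of the primary rule, and it does not reproduce. An error there could mean that the cut-off, the sample size or the method differs from what is stated.
2. A 50% goal at month 7 corresponds naturally to a comparator median of 7 months. If the published median were nearer 6 months, more than half of conventionally treated patients might be in remission by month 7. The 0.40 threshold would then sit further below standard therapy than the 10-point margin suggests.
3. A reader of Section 2 alone could take a pass at 26/49 as formal non-inferiority to phlebotomy or hydroxychloroquine, which the one-sample test does not assess.

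**Working it through.** **Inputs.** N = 49, cut-off 26, null rate 0.40, one-sided level 0.05, assumed true rate 0.58 and an exact binomial test, all from Section 6.

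**Step 1: Table 3.** The formula is P(X ≥ 26) = Σ C(49,k) p^k (1−p)^(49−k), summed over k = 26 to 49.

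| True rate | Printed | Exact |
|---|---|---|
| 0.40 | 0.0434 | 0.043856 |
| 0.45 | 0.1609 | 0.160905 |
| 0.50 | 0.3877 | 0.387725 |
| 0.55 | 0.6627 | 0.662671 |
| 0.60 | 0.8718 | 0.871845 |
| 0.65 | 0.9695 | 0.969466 |

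At 0.58 the exact power is 0.801509, matching the stated 80.2%. Five rows agree to four decimals. The 0.40 row should read 0.0439, and the gap is 0.043856 − 0.0434 = 0.000456.

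**Step 2: is the printed value a sign of another method?** At a true rate of 0.40 the mean is 49 × 0.40 = 19.6 and the SD is √(49 × 0.24) = 3.429.

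- Normal approximation with continuity correction: z = (25.5 − 19.6)/3.429 = 1.72, tail 0.0427.
- Without the correction: z = (26 − 19.6)/3.429 = 1.87, tail 0.0310.
- Mid-p: 0.0335.
- N of 47, 48, 50 or 51 with cut-offs of 25 to 27: none gives 0.0434. The nearest are 0.0460 (25 of 47) and 0.0418 (27 of 51).
- Reaching 0.0434 with 26 of 49 would need a true rate of 0.39966.

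With every other row exact, an isolated wrong digit is the most plausible explanation.

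**Step 3: does the decision rule stand?** The exact one-sided lower bound for x successes is the 5% quantile of Beta(x, 49 − x + 1).

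| Successes of 49 | P(X ≥ x) at 0.40 | Lower bound |
|---|---|---|
| 25 | 0.0776 | 0.3847 |
| 26 | 0.0439 | 0.4043 |
| 27 | 0.0231 | 0.4241 |

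The smallest count that keeps the error at or below 0.05 is 26. It is also the smallest whose bound exceeds 0.40, so the count rule and the confidence-bound rule agree. With the cut-off re-chosen for each N, no N from 30 to 48 reaches 80% power at 0.58 (the best is 0.7933, at N = 47). N = 49 gives 0.8015, so the sample size stands.

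**Step 4: the median.** A statement of 7 months and a range of 6 to 7 months are compatible at 7. To size the worst reading, assume exponential remission times (an illustration, not a figure from the plan). The proportion in remission at month 7 is then 1 − 2^(−7/m) for median m. A median of 7 gives 50.0% and a median of 6 gives 55.5%, so 0.40 would lie 10.0 to 15.5 points below the comparator rate. That range concerns how the goal is read against history. It does not enter the test, whose null rate is fixed at 0.40.

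**Step 5: the aim against the test.** Section 2 states the general aim. Section 6 states the only inferential rule, whose declaration refers to the performance goal, and it makes the comparison of medians descriptive. Where the inference is defined, the claim is already the narrower one.

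**The case for a change.** The strongest case for acting is that the Type I error of a primary rule should be printed correctly, that the printed figure understates it, and that correction costs one digit. The arithmetic is not in dispute: the entry is wrong as it reads. But it is descriptive. The decision is taken from the exact bound or the count of 26, and both are correct.

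On the median, it can fairly be said that one citation should be reported one way, and that a median below 7 months would weaken the link between the 50% goal and standard therapy. The first part stands as an editorial preference. The second is conditional on a study that cannot be consulted here. Nor does it follow strictly: a Kaplan-Meier curve is a step function and can reach 50% before month 7 and stay flat. The goal also has a second stated basis, the investigators' consensus about 7 months, which does not depend on the exact published median.

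On Section 2, the aim is broader than the test. However, rewording it would add nothing that Section 6 does not already fix, and it would leave similar general language elsewhere, such as the Section 4 statement that response rates will be compared with published results.

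**Conclusion.** No change to the plan follows. The 0.40 entry in Table 3 is a clerical slip of 0.0005 (0.0434 printed, 0.0439 exact). The error rate stays below 0.05, and N = 49, the 26/49 rule, the 80.2% power and the 0.40 bound are all confirmed. The digit can be checked against the source page and corrected whenever the document is next edited, and the median could be worded alike in Sections 4 and 6 at the same time. Neither affects what the trial does or may conclude. No error in the 50% goal or the 0.40 threshold has been shown, and the declaration is already limited to the performance goal.

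This rests on two assumptions: the tabulated probabilities refer to 49 observed binary outcomes, as the table header implies, and the cited study's median lies somewhere in the 6 to 7 months that the plan reports.

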7.1 Registration

Registration of participants on this protocol will employ an interactive data system in which the clinical site will attest to the participant's eligibility as per protocol criteria and obtain appropriate informed consent. CIRB approval for the protocol must be on file at the DMCC before accrual can occur from the clinical site.

The DMCC will use a system of coded identifiers to protect participant confidentiality and safety. Each participant enrolled will be assigned a local identifier by the enrollment site. This number can be a combination of the site identifier (location code) and a serial accession number. Only the registering site will have access to the linkage between this number and the personal identifier of the subject. At time of enrollment, each subject is registered through the DMCC provided web-based registration system. A unique participant ID will be generated at the time of enrollment, which will allow for a common ID to link a participant to multiple studies. Thus each participant will have two codes: the local one that can be used by the registering site to obtain personal identifiers and a second participant ID. For all data transfers to the DMCC both numbers will be required to uniquely identify the subject. In this fashion, it is possible to protect against data keying errors, digit transposition or other mistakes when identifying a participant for data entry since the numbers should match to properly identify the participant.

7.2 Data Entry

Study data will be entered into an electronic data capture (EDC) system supported by the DMCC. The EDC system is hosted in a secure, cloud-based environment managed by the DMCC, and complies with all applicable guidelines to ensure patient confidentiality, data integrity, and reliability. All data management best practices including quality controls and data validation procedures will be applied to ensure the validity and accuracy of the clinical database.

8. Human Subjects

8.1 GCP Statement

This clinical trial will be conducted in accordance with the ethical principles that have their origin in the Declaration of Helsinki, and that are consistent with Good Clinical Practice and all applicable regulatory requirements.

8.2 Benefits

Benefits of taking part include especially the opportunity for eligible subjects to receive Harvoni at no cost to them or their insurance carriers and to receive frequent and careful follow-up during and after this course of therapy. This is expected to lead to cure of HCV infection in the great majority of subjects. It may also lead to resolution of PCT.

The potential benefits of this protocol are felt by the investigators to outweigh the risks.

8.3 Risks

The potential risks of this study are:

- 1) Side effects of Harvoni: the most frequent side effects have been fatigue and headache, which have been of low severity.
- 2) Blood Draw: Needle insertion can cause pain and bruising at the site of insertion. Rarely fainting caused by a vasovagal response to the phlebotomy procedure may occur. Because the skin is penetrated by the needle, there is a low risk for infection at the venipuncture site. The amount of blood needed for each study visit (8mL tubes) is within approved safety limits. For any participant who has a medical condition that restricts their capacity to provide adequate sample volume, the number of tubes of blood obtained will be modified on an individual basis.
- 3) Loss of confidentiality: The risk of loss of confidentiality is low because as there are many safe guards in place. Conceivably, data including clinical and diagnostic information could be accidentally divulged. If such an event occurred, subjects might be at risk for discrimination by life or health insurance companies, by employers, and by adoption agencies. The Genetic Information Non-Discrimination Act (GINA) is a federal law that protects Americans from being treated unfairly because of differences in their DNA that may affect their health. This law prohibits genetic discrimination in the workplace and by health insurers. However, it provides no such protection for life insurance and disability insurance.

